**NOTE: due to the study status, the safety population will be used for all summary tables.**

## **7. PLANNED ANALYSES**

### **7.1 Interim Analysis**

For Phase 1b and dose expansion, safety data will be monitored continuously per standard Phase 1 oncology study practices.

For Phase 2, because the Simon 2-stage minimax design will be employed, response rate data will be assessed after Stage 1 and Stage 2 have been enrolled.

### **7.2 Final Analysis**

The final tables, listings, graphs, and data analysis will be conducted once all participants have completed the Phase 1b / Dose Expansion part of this study and the clinical database has been locked. Due to the differences in study design and for timeline purposes, Phase 2 will be analyzed and presented separately from Phase 1b / Dose Expansion. The clinical database for Phase 2 will be locked prior to the Phase 2 final tables, listings, graphs, and data analysis.

**NOTE: For this study, the database will be locked with 20 patients enrolled.**

## **8. DATA PRESENTATION AND HANDLING**

### **8.1 General Summary Table and Individual Patient Data Listing Considerations**

Summary tables for Phase 1b part of this study (the only part with enrollment) will be organized with respect to dose cohort and presented as:

Cohort 1 20mg/m2 (N=3)	Cohort 2 30mg/m2 (N=3)	Cohort 3 45mg/m2 (N=3)	Cohort 4 60mg/m2 (N=4)	Cohort 5 AZA 75mg/m2 + Alvocidib 75mg/m2 (N=3)	Cohort 6 AZA 75mg/m2 + Alvocidib 90mg/m2 (N=4)	Total (N=20)
------------------------------	------------------------------	------------------------------	------------------------------	--	--	-----------------

Alvocidib Phase 1b dose escalation cohort (from low to high) and Total.

Row entries in post text tables are made only if data exists for at least one patient (e.g., a row with all zeros will not appear). The only exception to this rule will apply to tables that summarize the study termination status of patients (e.g., reasons for not completing the study). In this case, zeros will appear for study termination reasons that no patient satisfied. The summary tables will clearly indicate the number of patients to which the data apply and unknown or not performed are distinguished from missing data.

Adverse event preferred terms and body/organ systems and medical history conditions will be coded using the Medical Dictionary for Regulatory Activities (MedDRA®) dictionary Version 21.0 (or later).

Listings will also be sorted by cohort (where applicable) and patient number. Listings will also include visit number, visit date/time and days relative to the initiation of study treatment.

In general, missing data will not be imputed unless otherwise specified. Any imputed or derived data will be flagged in the individual patient data listings. Imputed data will not be incorporated into any raw or primary datasets. These data will be retained in derived analysis datasets.

### **8.2 General Summary Table and Patient Data Listing Format Considerations**

The tables and listings will be numbered as closely as possible to the ALV-201 and ALV-202 abbreviated clinical study report tables/listings. Each table and listing title will be complete, accurate and concise. The last line of the title will provide the analysis group being summarized (e.g., Safety Population). Variables being summarized, and statistics reported will appear in the left most column(s) of a table. The next columns to the right should report the treatment arm data for the dose cohorts (1-6, low to high).

### **8.3 Data Management**

All data will be recorded by the site in individual source documents. An eCRF will be created by the data management group for recording of the required data in the study database. All eCRF information is to be filled in by site staff. If an item is not available or is not applicable, this fact should be indicated. Blank spaces should not be present unless otherwise directed.

The study monitor will perform source data verification of data entered into the eCRF and raise queries for correction by the site. The data entered into the eCRF will be patient to data validation checks for consistency and completeness by the data management group. Data queries will then be generated and sent to the investigational site for response before the database is locked and released for statistical analysis.

Database build, AE coding, medication coding, data cleaning will be conducted according to the Vantage Data Designs Data Management Plan for this specific study.

Derived datasets will be created using SAS® software. Data analyses and summary tables will be generated using the currently supported version at the time of data analysis (currently version 9.4).

### **8.4 Data Presentation Conventions**

Continuous safety variables (e.g., clinical laboratory values and vital signs) will be listed to the same precision as the source data. Derived variables will be calculated and listed using the same precision as the value(s) from which they were derived.

For the tabular reporting of descriptive statistics:

- Continuous variables: the same number of decimal places as in the raw data will be presented when reporting minimum and maximum, 1 more decimal place than in the raw data will be presented when reporting mean and median, and 2 more decimal places than in the raw data will be presented when reporting SD.
- Categorical/discrete variables: the frequency count and the percentage (of available data) for each class of the variable will be presented and will be displayed in the form XX (XX.X%) where the percentage is in the parentheses. All percentages will be presented to 1 decimal place, unless otherwise specified. Percentages equal to 100 will be reported as 100% and percentages will not be presented for zero frequencies. Unless otherwise specified, percentages will be calculated based on the number of patients specified by the appropriate population definition.

- Date variables: formatted as DDMMYY for presentation. Time will be formatted in military time as HH:MM for presentation.

Extra measurements (such as unscheduled or repeat assessments) will not be included in summary tables but will be included in patient listings. They will be used in summary tables which are not ‘time specific’, for example, summaries of maximum post dose values.

All tables, listings, figures will be produced in landscape orientation using Times New Roman 9-point font. Output files will be created in rich text file (RTF) format.

Missing or invalid data will be generally treated as missing, not imputed, unless otherwise stated (see Section 9.5).

The table, figures and listing shells and table of contents as part of this SAP provide the expected layout and titles of the tables, listings and figures. Any changes to format, layout, titles, numbering, or any other minor deviation will not necessitate a revision to the SAP nor will it be considered a deviation from planned analyses. Only true differences in the analysis methods or data handling will necessitate such documentation. The appropriate listings supporting the tables will be included and are not specified in the individual sections throughout the document.

Minor modifications may be necessary to the planned design of tables, listings and figures to accommodate data collected during the actual study conduct. Any major deviations from the final approved SAP (e.g., change in the population used, change from statistical method/assumption listed, transformation of data type [e.g., continuous data transformed to categorical], exclusion of planned analysis, etc.) or additional unplanned analyses will be documented (with justification) in the CSR.

## **8.5 Treatment Comparisons**

The following labels for dose level will be used on all tabulations, in the following order:

Cohort 1 20mg/m  (N=3)	Cohort 2 30mg/m  (N=3)	Cohort 3 45mg/m  (N=3)	Cohort 4 60mg/m  (N=4)	Cohort 5 AZA 75mg/m  + Alvocidib 75mg/m  (N=3)	Cohort 6 AZA 75mg/m  + Alvocidib 90mg/m  (N=4)	Total (N=20)
--	--	--	--	--	--	-----------------

## **8.6 Definitions, Computations, Derived Data**

- Screening: Screening is defined as ≤ 14 days prior to Cycle 1 Day 1 prior to the first study drug administration.
- Baseline: Measurements taken at Screening or prior to receiving the first dose of study drug; whichever is latest.

- Dose Limiting Toxicity (DLT) is defined as
  - Any Grade 5 toxicity that is not clearly and incontrovertibly related to the underlying disease or extraneous causes
  - Any Grade 4 nonhematologic toxicity considered at least possibly drug related
  - Grade 4 neutropenia lasting  $\geq$ 42 days from the start of a cycle in the absence of evidence of active disease
  - Any AST or ALT elevation  $\geq$ 3x ULN accompanied by serum
  - bilirubin levels  $>$ 2x ULN
  - Any Grade 3 nonhematologic toxicity considered at least possibly drug related and that does not resolve to  $\leq$ Grade 2 within 48 hours, with the following exceptions:
    - Grade 3 bilirubin, AST, ALT or alkaline phosphatase will be considered dose-limiting only if resolution to  $\leq$ Grade 2 requires more than 7 days
    - Grade 3 diarrhea, mucositis, nausea, or vomiting will be considered dose limiting only if resolution to  $\leq$ Grade 2 (including use of supportive care) requires more than 7 days
    - $\geq$ Grade 3 creatinine elevation that does not resolve to  $\leq$ Grade 2 within 7 days
    - Anorexia, fever, neutropenic fever, and infections of any grade
    - Bone marrow hypoplasia that occurs for  $>$ 42 days with bone marrow (BM) cellularity  $\leq$ 5% and no evidence of MDS/leukemia. Bone marrow disease assessments conducted per protocol on Day 28 ( $\pm$ 3 days) of every even cycle may be used to guide this decision.
- The MTD is defined as the dose at which  $\leq$ 1 of 6 patients experience a DLT during Cycle 1 with the next higher dose having at least 2 of 3 to 6 patients experiencing a DLT during Cycle 1. Adverse events meeting the definition of DLT during Cycles 2+ will be taken into consideration when evaluating dose escalation.
- 1 year = 365.25 days. Year is calculated as (days / 365.25) and will be rounded to 1 digit after the decimal point (tenths) for presentation purposes;
- 1 month = 30.4375 days. Month is calculated as (days / 30.4375) and will be rounded to 1 digit after the decimal point (tenths) for presentation purposes;
- 1 pound = 0.454 kg and 1 kg = 2.2 pounds;

- 1 inch = 2.54 cm and 1 cm = 0.3937 inches;
- Body mass index (BMI) calculated as [weight (lbs) / height (in)] x 703;
- Age will be calculated in years relative to the date of study consent based on the following SAS statement: Age = ([Consent Date - Date of Birth] / 365.25) and will be rounded to 1 digit after the decimal point (tenths) for presentation purposes.

## **9. GENERAL CONSIDERATIONS FOR DATA ANALYSES**

The listings, figures and summary tables for the disposition and safety, and efficacy data will be the responsibility of the study Biostatistician at Vantage Data Designs.

The currently supported version of SAS software (9.4 or later) will be used to perform all data analyses. The actual SAS version used will be presented in the Clinical Study Report.

All data in the database will be presented in the data listings. Unless otherwise stated, all listings will be sorted by dose cohort (where applicable), patient number and assessment date/time.

Unless otherwise stated, continuous variables will be summarized using descriptive statistics including number of non-missing observations, mean, standard deviation, median, minimum and maximum values. Categorical variables will be summarized with frequency counts and percentages. The population size (N for sample size and n for available data) and the percentage (of available data) for each class of the variable will be presented.

### **9.1 Multicenter Studies**

Data from all participating sites will be pooled for the analysis.

### **9.2 Other Strata and Covariates**

Not applicable for this study.

### **9.3 Examination of Subgroups**

Not applicable for this study.

### **9.4 Multiple Comparisons and Multiplicity**

Not applicable for this study.

### **9.5 Missing Data and Dropouts**

The issue of how to handle missing data caused by dropouts in clinical studies is a research topic that is still under development in the statistical literature. As has been noted in the ICH-

E9 guideline, “no universally applicable method of handling missing values can be recommended”. The best approach is to minimize the chance of dropouts at the design stage of the clinical study and during study monitoring.

In general, data will be analyzed as received from the clinical database. Hence, missing values will not be replaced by imputed values except for the following situations:

#### **9.5.1 Adverse Events**

Adverse events with missing or partial dates will be handled such that in the absence of contradictory information an AE is classified as “treatment emergent”.

#### **9.5.2 Concomitant Medications**

Medications with missing or partial dates will not have dates imputed and will presented as collected in the patient listings.

#### **9.5.3 Other Situations**

For patients who are withdrawn from the study prior to study completion, all data compiled up to the point of discontinuation will be used for analysis. All withdrawals will be included in all analyses up to the time of withdrawal.

### **10. STUDY POPULATION**

All disposition, baseline and demographic analyses will be conducted on the Safety population.

#### **10.1 Patient Enrollment and Disposition**

Enrollment and disposition will be summarized for all enrolled patients (defined as those patients who signed informed consent form). The summary of enrollment will be presented by investigator site. The patient disposition summary will include:

- The number of patients who were enrolled at each study center.
- Number of patients in the safety analysis set.
- A summary of patient dose cohorts.
- A summary of patients who complete the protocol.
- A summary of primary reason for discontinuation from study.

A listing of patient enrollment and disposition will be provided for all enrolled patients. A listing of whether or not all inclusion and exclusion criteria were met and if not, which criteria were not met, by patient, will also be presented.

## **10.2 Protocol Violations or Deviations**

Protocol deviations were not collected per the eCRFs.

## **10.3 Demographics**

Demographic characteristics will include age, age category (18-25, 26-35, 36-45, 46-55, 56-65, >65 years), sex, race, ethnicity, and ECOG Performance Status.

The categorical (discrete) variables will be summarized using counts and percentages. The continuous variables will be summarized using mean, median, standard deviation, and range (maximum, minimum). All demographic data will be listed by patient.

## **10.4 Initial Diagnosis / Current Disease Status**

Initial diagnosis / current disease status outputs will include time from initial diagnosis to informed consent (months), MDS type, prior therapy for MDS, IPSS-R score, 2016 WHO classification, and best response to prior MDS treatment.

The categorical (discrete) variables will be summarized using counts and percentages. The continuous variables will be summarized using mean, median, standard deviation, and range (maximum, minimum). All baseline characteristics data will be listed by patient. Medical history and childbearing potential will be listed only

## **10.5 Medical History**

The incidence of Medical history will be summarized by system organ class (SOC) and preferred term (PT) using MedDRA version 21.1. In the summary tables, patients may be counted under multiple system organ class (SOC) and preferred terms (PT), but for each SOC and PT category, patients will be counted only once. All medical history data will be presented in patient listings.

## **10.6 Concomitant Medications**

Prior medication and concomitant medications will be presented in patient listings only.

## **10.7 Study Drug Administration and Exposure**

Study drug administration and exposure will be summarized by number of treatment cycles completed and the number of weeks on study. The categorical (discrete) variables will be summarized using counts and percentages. The continuous variables will be summarized

using mean, median, standard deviation, and range (maximum, minimum). All study drug administration data will be listed by patient.

## **11. EFFICACY ANALYSIS**

The response criteria for this study are from the Revised International Working Group (IWG) Response Criteria (2006). These criteria are described in detail in Appendix F of the protocol.

Response categories include CR: Complete Response, CR marrow: Marrow CR, PR: Partial Remission, Stable Disease, Failure, Relapse after CR or PR, and Not Evaluated / Missing.

The best objective response for each patient will be summarized by number and percentage.

In addition, cytogenetic responses were collected and include: Complete, Partial, Stable Disease, Failure – Death, Failure – Disease Progression, and Response Not Available. The best cytogenetic response for each patient will be summarized by number and percentage.

Hematological Improvement responses were collected and include N/A, Erythroid Response, Platelet Response, Neutrophil Response, Progression or Relapse after HI, and Response Not Available. Because these data were collected as ‘check all that apply’ (instead of select one), hematological improvement data will be presented in patient listings format.

In addition to the summary tables, efficacy data will also be presented in the individual patient listings.

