5.2.2.6 Cycles 2+ – Day 28 (+1/-3 Days)

Perform the following evaluations on Day 28 of every EVEN cycle (ie, Cycle 2, Cycle 4, etc):

- Perform bone marrow biopsy and aspiration and collect peripheral blood sample for assessment of response ([Appendix F](#)), standard cytogenetics, and PD analyses ([Section 7.4](#), [Table 9](#) and [Table 10](#);

Appendix E). [Note with a +1/-3 day window, these may be performed on Days 25-28 or Day 1 of the next cycle. If performed on Day 1 of the next cycle, please collect bone marrow and aspiration as well as peripheral blood samples prior to administering first dose of DEC or AZA]

- If the bone marrow biopsy and/or aspirate is nonproductive or not diagnostic, at the EVEN 2+ cycle visits, there should be no delay in dosing and the procedure should be repeated within 7 days.
- Six to 8 bone marrow slides will be prepared (in addition to fresh bone marrow samples) and sent to the Sponsor.
- Response assessments **with** standard cytogenetics **and** blood sample collection for PD analyses should be repeated on Day 28 (+1/-3 days) of Cycles 2, 4, and 6, and then every 4 cycles, thereafter, or as clinically indicated. If medically appropriate, response assessments should be repeated at the time of disease progression.
- Assess for AEs
- Record only those medications (prescription, nonprescription, nutritional supplements) administered in conjunction with an AE.

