11.9 EFFICACY ANALYSIS

The efficacy endpoints include the following:

- Complete Response Rate (CRR) is the percentage of patients achieving a CR, CRi, CRmarrow, PR, or HI. Patients who, for any reason, do not supply bone marrow for response assessment are counted among those not achieving CR/CRi/CRmarrow/PR/HI. CRR will be summarized by number and percentage of patients meeting the definition of CRR along with the corresponding exact 95% confidence intervals.
- Duration of response and time to AML will be summarized by Kaplan-Meier methods (median, 95% CI, number of events, number censored, and Kaplan-Meier figures),
- Hematological improvement and rate of transfusion independence will be summarized using the appropriate descriptive statistics and 95% confidence intervals.
- Overall survival (OS), defined as the time from first dose to death from any cause. OS will be summarized by Kaplan-Meier methods (median, 95% CI, number of events, number censored, and Kaplan-Meier figures).

Descriptive statistics will also be calculated for each secondary measure of efficacy.

- The proportion of MDS patients in the overall population achieving RBC transfusion independence with duration ≥ 84 days (12 weeks) during treatment. Baseline RBC transfusion dependency is defined as an average transfusion requirement of ≥ 2 units/28 days of RBCs without any consecutive 28-day gaps between transfusions for a minimum of 56 days immediately preceding first dose. Transfusion data include the hemoglobin value for which the transfusion was administered and must have been ≤ 10.0 g/dL within 7 days prior to transfusion administration to be counted toward the RBC transfusion-dependent status.
- Platelet transfusion independence with duration ≥ 84 days (12 weeks) will be assessed in the proportion of patients who were platelet transfusion-dependent at baseline. Baseline platelet transfusion requirements are established by the number of platelet transfusions administered during the 56 days immediately preceding and including the date of first dose.

- Erythroid hematologic improvement and platelet hematologic improvement will be assessed according to the 2006 revised IWG criteria [28].

Additional analyses may be performed to assist the sponsor in planning future studies.

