#### **3.2 Phase 1b Secondary Objectives:**

- To determine the Complete Response Rate ([CRR]: Complete response [CR] / Complete Response with Incomplete blood count recovery [CRI] / CR in marrow / Partial Response [PR] / Hematologic Improvement [HI])
- To determine if treatment with alvocidib administered in sequence after DEC (during dose escalation) or AZA results in improvements in transfusion dependence (defined as an average transfusion requirement of  $\geq 2$  units/28 days of RBCs without any consecutive 28-day gaps between transfusions for a minimum of 56 days immediately preceding first dose) and/or hemoglobin level (transfusion data to include the hemoglobin value for which the transfusion was administered and must have been  $\leq 10.0$  g/dL within 7 days prior to transfusion administration to be counted toward the RBC transfusion-dependent status):
  - Hemoglobin increase of  $\geq 1.5$  g/dL without erythropoietin-stimulating agents (ESAs)

OR

- Reduction of  $\geq 4$  RBC transfusions/8 weeks in comparison to pre-treatment values and lasting at least 8 weeks

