- Incidence of Treatment-Emergent Grade 3, Grade 4, and Grade 5 Adverse Events Judged Possibly, Probably or Definitely Related to the Study Drug Regimen by MedDRA System Organ Class and Preferred Term (Safety Population)

In the summary tables, patients may be counted under multiple system organ class (SOC) and preferred terms (PT), but for each SOC and PT category, patients are only counted once. If a patient has the same AE on multiple occasions, the highest severity grade (fatal > life threatening > severe > moderate > mild) or drug relationship (related > possibly related > not related) recorded for the event will be summarized.

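### SAP 3.2 keeps CRR, which includes hematologic improvement, as a Phase 1b secondary objective, but the text of SAP 11 derives no composite CRR and puts HI in listings only

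*SAP*

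**What the plan says.** The first Phase 1b secondary objective in SAP 3.2 opens "To determine the Complete Response Rate ([CRR]: Complete response [CR" and goes on to list CRi, CR in marrow, PR and HI as the other ways to qualify. Protocol 3.1 has the same objective.

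Protocol 11.9 gives the analysis: "CRR will be summarized by number and percentage of patients meeting the definition of CRR along with the corresponding exact 95% confidence intervals". It adds that patients who for any reason "do not supply bone marrow for response assessment are counted among those not achieving" a qualifying response. It also plans descriptive statistics and 95% confidence intervals for HI.

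SAP 11 sets out a different table: "Response categories include CR: Complete Response, CR marrow: Marrow CR, PR: Partial Remission, Stable Disease, Failure, Relapse after CR or PR", followed by a Not Evaluated / Missing category. Best objective response over these categories is given as number and percentage, as is best cytogenetic response. HI was collected in a field that allowed several ticks, and for that reason "hematological improvement data will be presented in patient listings format". SAP 11 does not name CRR.

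SAP 1 and SAP 15.1 say that early closure with 20 patients removes inferential methods. Both keep the descriptive tables and the listings for a synoptic report.

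**The concern.** The SAP states an objective that its own analysis text does not answer as defined. HI is one of the five ways to be a CRR responder, and no planned table in SAP 11 shows it.

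A patient with HI but less than PR, who supplied marrow for response assessment, is a responder under protocol 11.9. The planned best-response table does not count that patient as CR, marrow CR or PR. A reader who adds those three rows gets a rate for a narrower endpoint than the one in SAP 3.2. A reader who tries to rebuild CRR from the listings finds no rule in the SAP text for the denominator, for patients without marrow, or for CRi. Two careful readers could therefore report different rates.

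**Working it through.** The plan states no figure for this endpoint, so the check is mainly a comparison of text, followed by simple arithmetic.

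**1. Objective against analysis.**
- CR, marrow CR and PR: in the CRR definition (SAP 3.2) and in the SAP 11 table.
- HI: in the definition, but in listings only.
- CRi: in the definition, but not an SAP 11 category. This gap starts in the protocol, because the Appendix F response criteria contain no CRi entry.
- The composite: in the definition and in protocol 11.9, but not in SAP 11.

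**2. Does the multiple-tick format prevent a count?** No. SAP 12.1 handles the same data structure for adverse events: a patient may appear under several terms, but "for each SOC and PT category, patients are only counted once". A yes/no flag per lineage, and one for any lineage, follows the same logic. The HI field does need a rule, because SAP 11 shows that it also holds N/A, Response Not Available, and Progression or Relapse after HI. Appendix F also requires HI to last at least 8 weeks, and the SAP does not say whether a tick already reflects that.

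**3. Is the change documented?** SAP 11 gives its reason for listing HI. SAP 16 has only a general statement that the SAP takes precedence over the protocol's statistical section. Neither says that CRR is dropped. Protocol 11.1 allows the SAP to modify planned analyses, provided the change is clearly documented there.

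**4. Which HI-only patients are affected?** Under protocol 11.9, only those who supplied marrow; an HI-only patient without marrow is a non-responder either way. Protocol 5.2.2.6 schedules marrow with the instruction "Perform the following evaluations on Day 28 of every EVEN cycle", so the first on-study sample falls at the end of Cycle 2. With 28-day cycles and no delay that is 2 × 28 = 56 days, or 8 weeks. Since HI must also last 8 weeks, an HI-only patient will often have supplied marrow, but not always. This is inference from the schedule, not data.

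**5. Size per affected patient.** Cohort sizes in SAP 1 are 3 + 3 + 3 + 4 = 13 (decitabine) and 3 + 4 = 7 (azacitidine), in total 13 + 7 = 20, which matches the stated total. Assuming all 20 were treated, one HI-only patient with marrow moves the rate by 1/n:
- overall: 1/20 = 5.0 points
- decitabine cohorts: 1/13 = 7.7 points
- azacitidine cohorts: 1/7 = 14.3 points
- a cohort of 4 or 3: 1/4 = 25.0 or 1/3 = 33.3 points
- an HI-only patient without marrow: 0 points

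**6. Illustration with assumed counts.** Exact (Clopper-Pearson) limits for x of n are the 0.025 quantile of Beta(x, n − x + 1) and the 0.975 quantile of Beta(x + 1, n − x).
- 4 of 20 with CR, marrow CR or PR: 20% (5.7% to 43.7%)
- plus 2 HI-only patients with marrow, 6 of 20: 30% (11.9% to 54.3%)
- plus 4 such patients, 8 of 20: 40% (19.1% to 63.9%)

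Within cohorts the intervals say almost nothing: 1 of 3 gives 0.8% to 90.6%, and 1 of 4 gives 0.6% to 80.6%. The need is for n/N (%); the interval adds little.

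**The case against.** The strongest reply has four parts.

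*The SAP supersedes the protocol.* SAP 1 and SAP 16 say so, and SAP 11 openly explains the HI listing. This stands as far as it goes: the sponsor may drop a protocol analysis. It does not settle the point, because the mismatch is inside the SAP itself (3.2 against 11) and the loss of the composite is not recorded.

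*Protocol 11.9 may not be a Phase 1b rule.* The protocol synopsis and SAP 3.7.2 put the efficacy endpoints under Phase 2, and some of the 11.9 items, such as overall survival, depend on follow-up that protocol 5.4.2 provides for Phase 2 only. This is a fair doubt. However, CRR is a Phase 1b objective in both documents, protocol 11.1 plans results by phase and dose level, and 11.9 is the only place that says how to summarise CRR.

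*The table shells may contain a CRR table.* SAP 8.4 says: "The table, figures and listing shells and table of contents as part of this SAP provide the expected layout and titles". The shells are not in the text available here, so this cannot be ruled out.

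*Little depends on it.* The study is closed, no inference is planned, cohorts hold 3 or 4 patients, and the response and HI data are listed by patient. The number of HI-only patients may be zero. All of this stands, and it limits the severity.

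**Conclusion.** The point holds for the SAP text: a retained Phase 1b secondary objective has no composite CRR and no HI count in SAP 11, the reason given for listing HI does not prevent counting, and the omission of CRR is not recorded. It is a reporting and documentation gap of modest severity that should be fixed. It does not threaten a confirmatory result.

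The size is 5 points on the overall rate for each HI-only patient with marrow, if all 20 enrolled patients were treated and the no-marrow rule of protocol 11.9 applies. The total effect is unknown, because the documents give no count of such patients.

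Three stronger readings are not supported:
- A reader might infer that the report will tabulate nothing for this objective. The best-response table does report CR, marrow CR and PR, three of the five components, and a fourth, CRi, has no criteria to score.
- A reader might infer that every HI-only patient is lost from CRR, or that the data are lost. Those without marrow are non-responders by rule, and HI remains in the listings.
- A reader might infer that an HI count would also answer the transfusion and hemoglobin objective in SAP 3.2. It would not by itself. That objective uses a 10.0 g/dL cutoff to define baseline transfusion dependence, whereas the 9.0 g/dL cutoff in Appendix F applies only to the transfusion-reduction route of erythroid HI.

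**What to change.** In SAP 11, before database lock:

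1. Derive per-patient flags for erythroid, platelet, neutrophil and any HI: positive if that response was ticked at any visit. N/A, Response Not Available, and Progression or Relapse after HI do not themselves count as a response. State whether a tick already reflects the 8-week duration in Appendix F.
2. Derive CRR per patient under the protocol 11.9 rule, with no marrow scored as non-response.
3. Tabulate CRR and HI by lineage as n/N (%) by cohort and total, in the safety population that SAP 6 sets for all summary tables. Keep Not Evaluated / Missing in the denominator.
4. Treat the exact 95% interval as optional. Show it as descriptive only, or record its omission.
5. State that CRi is not scored separately because Appendix F has no criteria for it.
6. Record in SAP 16 any protocol 11.9 analysis that is dropped.

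If the shells already hold a CRR table, the text of SAP 11 should be brought into line with it. The cost is a few derived flags with a short rule for the check boxes, one descriptive table from data already collected, and short entries in SAP 11 and SAP 16.
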